Appendix 1 – Information with regards to Safety Reporting in Non-CTIMP Research

	Who	When	How	To Whom
SAE	Chief Investigator	Within 15 days of CI becoming aware of the event	SAE Report form for Non-CTIMPs, available from NRES website.	Main REC with a copy to the sponsor
Urgent Safety Measures	Chief Investigator	Immediately Within 3 days	By phone Notice in writing setting out reasons for the urgent safety measures and the plan for future action.	Main REC Main REC with a copy sent to the sponsor. The MREC will acknowledge this within 30 days of receipt.
Progress Reports	Chief Investigator	Annually (starting 12 months after the date of favourable opinion)	Annual Progress Report Form (non-CTIMPs) available from the NRES website	Main REC with a copy to the sponsor
Declaration of the conclusion or early termination of the study	Chief Investigator	Within 90 days (conclusion) Within 15 days (early termination) The end of study should be defined in the protocol	End of Study Declaration form available from the NRES website	Main REC with a copy to the sponsor
Summary of final Report	Chief Investigator	Within one year of conclusion of the Research	No Standard Format However, the following Information should be included:- Where the study has met its objectives, the main findings and arrangements for publication or dissemination including feedback to subjects	Main REC with a copy to be sent to the sponsor

Appendix 2 – Study Poster

WANT TO LEARN HOW BABY IS PREPARING TO MEET YOU?

Help us evaluate a new group called Baby CHAT in this research project!

You may be eligible if you are:

- ✓ 20-34 weeks pregnant
- ✓ feeling low in mood

WHAT IS BABY CHAT?

Baby CHAT is a new group that helps you to learn how your baby is developing socially before birth.

The group uses the latest research, including video footage of babies during 4D ultrasound scans, to help you imagine how your baby is getting ready to socialise in the outside world.

The group will take place online with other pregnant parents. It will last for up to 90 minutes.

WHAT IS INVOLVED?

You will be asked to complete some brief online questionnaires before and after attending Baby CHAT, and 1 month later. The questionnaires will take around 10 minutes to complete each time.

Want to register or find out more?

Scan the QR code on the right (point your phone's camera at it and click the link), or email [contact] to receive more information or to express your interest

[figure not shown]
Study approved by NHS Research Ethics Committee

Poster version 2, 12/08/22. To be removed May 2023

[figure not shown]
  

Appendix 3 – Distress Pathway

Group facilitators will remain vigilant to signs of emotional distress in participants during the group. The content and methods of Baby CHAT allow for sensitive and validating group conversations regarding participants' emotional reactions during the group and therefore low levels of distress can be managed sensitively within the group setting.

Appendix 4 – Safeguarding pathway

Appendix 5 – Feedback Form

Participant ID:

Baby CHAT Group Feedback

Thank you for coming to Baby CHAT.

We would really like your feedback on Baby CHAT. Please let us know anything that you enjoyed as well as anything you think we could do to improve Baby CHAT.

Your feedback will add to our Baby CHAT research. We would like to include your feedback in our report about Baby CHAT. When we do this, we make sure that the feedback is completely anonymous so no one will know who has written the comments.

Date you attended Baby CHAT:

1. Did you think the timing of the group in your pregnancy was (please circle):

Too early

About right

Too late

Please explain your answer:

.....
.....
.....
.....

2. Was the length of the group (please circle):

Too long

About right

Too short

Please explain your answer:

.....
.....
.....
.....

3. What did you enjoy about the group?

.....
.....
.....
.....

4. What information did you find most useful from the group? Why?

.....
.....
.....
.....

5. Is there anything we can do to improve Baby CHAT?

.....
.....
.....
.....

6. Was the group relevant to people with low mood? Why/why not?

.....
.....
.....
.....

7. What did you think about the 4D scan video footage? Did this give you any ideas about how your own baby is developing?

.....
.....
.....
.....

8. Do you have any other comments or feedback on the group?

.....
.....
.....
.....

Thank you for taking the time to complete this questionnaire.

Appendix 6 – Feedback Form – Follow-Up

Participant ID:

Baby CHAT Group Feedback – Follow-Up

We would really like your feedback on whether Baby CHAT has been helpful over the weeks since you attended. Please let us know anything that you have noticed or remembered over the last few weeks.

Your feedback will add to our Baby CHAT research. We would like to include your feedback in our report about Baby CHAT. When we do this, we make sure that the feedback is completely anonymous so no one will know who has written the comments.

Date you attended Baby CHAT:

1. How much have you thought about Baby CHAT since attending (please circle):

A lot

Sometimes

Rarely/never

Please explain your answer:

.....
.....
.....

2. What have been the lasting impacts of Baby CHAT, if any:

.....
.....
.....

3. Do you think attending Baby CHAT has helped your mood? Why/why not?

.....
.....
.....

4. Do you have any other comments or suggestions about the impact of Baby CHAT over time? Is there anything else that might be helpful?

.....
.....
.....

Thank you for taking the time to complete this questionnaire.

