Women will be excluded if they are experiencing severe depression or current severe co-morbid diagnoses (e.g. psychosis), if they endorse 'yes, quite often' or 'sometimes' on question ten of the EPDS (in the past 7 days, 'the thought of harming myself has occurred to me'), or if they are unable to complete informed consent and the questionnaires in English. Participants must be able to sufficiently understand the psychoeducational materials and group discussions during the intervention, so that all participants experience a 'high feedback', interactive intervention.

There will be clear signposting to NHS and third sector organisations (including the general practitioner, midwifery team, local psychological therapies service, and other online resources) for all included and excluded participants, given that women interested in the study will be experiencing subjective low mood and may not be accessing treatment.

Withdrawal of subjects

Participants have the right to withdraw from the study at any time for any reason. If participants drop out during the study their data will be included in the analysis, unless they also withdraw consent for this. No further data will be collected from them. Their pseudonymised data will be destroyed after a period of 5 years following completion of the study, consistent with Clinical Trials Regulations and in line with the rest of the data collected in this study. Efforts will be made to report reasons for withdrawal. Withdrawn participants will not be replaced. Withdrawn participants will receive signposting information to local mental health and other support services, as outlined above (see Exclusion criteria).

Statistics

The following quantitative feasibility and acceptability outcomes will be collected: rates of eligible participants, uptake and retention of participants, scores on the feedback form, rates of missing data, and scores on the fidelity checklist (to monitor intervention delivery). For the qualitative arm of the study, participants will complete the open-ended questions on the feedback form. Descriptive data on participant demographic characteristics will also be collected.

The quantitative feasibility and acceptability outcomes outlined above will be summarised descriptively. Qualitative data from the open-ended questions on the feedback form will be analysed using content analysis.

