Although this study is exploratory due to the novelty of the intervention, within feasibility research it is appropriate to set a priori thresholds for the main feasibility and acceptability outcomes. Feasibility thresholds will be as follows: 30 or more potential participants express interest in the study (participant uptake); 20 or more participants attend Baby CHAT (participant retention); and at least 70% of participants complete the study measures (missing data). The acceptability of Baby CHAT will be assessed by the feedback form, which consists mostly of open-ended questions. These will be analysed qualitatively and therefore no specific acceptability thresholds will be set.

Effect sizes for primary and secondary outcome measures will be calculated using Cohen's d. These effect sizes will inform the sample size calculations of future larger-scale studies on Baby CHAT.

Items on the outcome questionnaires will be designated as mandatory on the online survey portal, Qualtrics, to minimise missing data. Participants will be contacted to attempt to complete any missing items from other forms. Therefore, no statistical imputation methods will be required to correct for missing data.

Any deviations from the original statistical analysis plan will be reported in a protocol amendment.

4. Study procedures

Informed consent procedure

All interested participants, whether they self-referred to the study or consented to be contacted via their clinician, will have an initial contact with the research team to ask any questions about the project. Participants will be sent a full Participant Information Sheet by email to read and consider. The information in the Participant Information Sheet and opportunity for further discussion with the research team will allow detailed explanation of the aims, methods, anticipated benefits and potential harms of the study, as well as the participants' right to refuse involvement in the study and to withdraw consent at any time. The research team will ensure adequate time for each participant to consider their consent to take part. Individuals who agree to take part will then be asked to complete and return a signed consent form. All participants will receive a copy of their signed consent form.

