The feedback questionnaire (Appendix 5) was developed as part of the initial trial on Baby CHAT with the general population (Cox et al., 2020). The form has been adapted for the purpose of this study and contains eight items, consisting of eight open-ended questions, two of which additionally have closed question components. The feedback form aims to gather participants' views on their experience of the group in order to develop it for future use, including what they liked about Baby CHAT, how helpful they found the inclusion of the 4D scan footage and anything they felt could have improved the group.

A brief, follow-up feedback form was developed for the purposes of this study's longitudinal component (Appendix 6). The form consists of four open-ended questions, one of which also contains a closed question component. The items aim to evaluate participants' experiences of the impact of the intervention over time, including anything they felt could improve the longitudinal impact and whether they have noticed any subjective changes in their mood.

Intervention

Baby CHAT is an approximately 90-minute group intervention to be delivered during pregnancy. The group is comprised of psychoeducational material about a baby's social development after birth and while the baby is growing in the womb. Attendees are encouraged to think about when an infant's social development begins and consider whether this occurs before or after birth. Participants are then shown a video clip of Reissland et al.'s (2016) study showing 4D ultrasound images of foetuses mouthing in response to sounds that are presented to them outside the womb. Reissland's research suggests that babies' social development may begin to occur as early as 32 weeks. During Baby CHAT, parents are encouraged to reflect on this information in the context of their own baby's development, including their likes and dislikes, routine and personality. The final section of the group involves generating ideas for social activities that parents can try with their baby prior to birth, such as singing to, massaging or reading to their baby. At the end, participants are asked to think about a positive take-home message from the session and, if they feel comfortable, to share this with the group. A Baby CHAT handout will be provided for participants to work through during the group and to refer to at home. See Appendix 7 for the full session plan.

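### Two feedback items presuppose a positive answer and no item asks directly about negative experience, so the acceptability analysis may lean favourable

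*Combined protocol and SAP*

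**What the plan says.** Acceptability is part of the primary objective (Section 2.1). Section 3, Statistics, names the instrument: "The acceptability of Baby CHAT will be assessed by the feedback form, which consists mostly of open-ended questions". It continues: "These will be analysed qualitatively and therefore no specific acceptability thresholds will be set". The method is given in the same section: "Qualitative data from the open-ended questions on the feedback form will be analysed using content analysis".

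Section 4, Baby CHAT Feedback Form, says that the post-intervention form "contains eight items, consisting of eight open-ended questions, two of which additionally have closed question components". Two of its items, as printed in Appendix 5, are:

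- Item 3: "What did you enjoy about the group"
- Item 4: "What information did you find most useful from the group? Why"

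The same part of Section 4 describes a four-item follow-up form, which is to cover, among other things, "whether they have noticed any subjective changes in their mood". The printed item (Appendix 6, item 3) is "Do you think attending Baby CHAT has helped your mood? Why/why not".

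Two further places give the form a safety role. Section 4, Risks/burdens, counts on it to help detect adverse events. Section 6 says that adverse events will be collected through it by asking participants about negative effects of the group.

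**The concern.** With no threshold, the acceptability conclusion depends on what women write, and what they write depends partly on what they are asked. A question that assumes enjoyment or usefulness invites a favourable comment even from someone who had little to praise. Favourable codes from items 3 and 4 are therefore weak evidence of acceptability unless a matching question invites the opposite.

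The protocol itself expects some negative reactions. Section 4, Risks/burdens, foresees guilt and distress and says they are more likely in this group than in the general population. If no question seeks such reactions directly, they may be under-reported in the acceptability findings and in the adverse event record. The secondary objective of developing the intervention from feedback (Section 2.1) also needs to know what did not work.

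**Working it through.** No sample size, power or error rate bears on this point. The check is a count and classification of every printed item.

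**Step 1: reproduce the stated counts.** Section 4 gives eight items for the post-intervention form, two with a closed part. Appendix 5 prints eight, with closed parts on items 1 and 2. Section 4 gives four items for the follow-up form, one with a closed part. Appendix 6 prints four, with a closed part on item 1. Both counts agree, so no item appears to have been lost from the printed forms. Total: 8 + 4 = 12.

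**Step 2: classify by wording.**

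| Form and item | Subject | Wording |
|---|---|---|
| Appendix 5, 1 | Timing in pregnancy | Two-sided closed options, plus reasons |
| Appendix 5, 2 | Length of group | Two-sided closed options, plus reasons |
| Appendix 5, 3 | Enjoyment | Presupposes a positive answer |
| Appendix 5, 4 | Most useful information | Presupposes a positive answer |
| Appendix 5, 5 | Improvements | Invites suggestions, so allows criticism |
| Appendix 5, 6 | Relevance to low mood | Two-sided, with reasons |
| Appendix 5, 7 | 4D footage | Neutral opening; second part leans positive |
| Appendix 5, 8 | Other comments | Neutral |
| Appendix 6, 1 | How often thought about | Graded frequency, plus reasons |
| Appendix 6, 2 | Lasting impacts | Allows for none |
| Appendix 6, 3 | Effect on mood | Positively worded, but accepts a no |
| Appendix 6, 4 | Other comments | Neutral; invites suggestions |

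**Step 3: count.**

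- Items that presuppose a positive answer: 2 of 8 on the post-intervention form (2/8 = 25%), or 2 of 12 overall (2/12 = 17%).
- Adding the positively worded mood item: 3 of 12 (3/12 = 25%).
- Items that ask directly about dislikes, unhelpful content, distress or worsening: 0 of 12.

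The classification is a judgement. The borderline cases are Appendix 5 item 7 (second part) and Appendix 6 item 1. Moving either does not change the zero.

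**Step 4: set the text against the forms.**

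- *Mood.* Section 4 describes a question on change of any kind. Appendix 6 item 3 asks about benefit. A woman can answer no, but she is not asked whether her mood became worse.
- *Negative effects.* Section 6 says the question will be put through the feedback form, and the Section 2.3 flowchart places adverse events at the post-intervention visit. Appendix 5, completed at that point, contains no such question, and neither does Appendix 6. These passages must be reconciled.

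**The case against.** The strongest reply is that the forms are not one-sided, and this largely stands. Six of the eight Appendix 5 items (1, 2, 5, 6, 7 and 8) leave room for criticism. Items 1, 2 and 6 expressly allow an unfavourable answer, and the form's introduction asks for improvements as well as for what was enjoyed. A reader might infer that the acceptability evidence as a whole comes from leading questions, or that the prompts admit only positive answers. The documents support neither. The mood item itself asks for reasons either way, and it sits on a form that Section 4 describes as evaluating impact over time, so it is at most secondary evidence of acceptability.

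It can also be said that worsening mood would be caught by the EPDS, repeated post-intervention and at one month (Section 2.3). That stands for symptom level. It does not show whether a woman attributes a change to the group, which is what the feedback item is for.

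Pressure to be polite can be argued both ways. The forms carry a participant ID and are addressed to the team running the group. They also promise anonymity in reporting, and the feedback is collected online through Qualtrics (Section 9). The documents do not show how much pressure remains.

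Finally, Section 6 does commit to asking about negative effects. That answers the concern only if the question is on the form, and it is not.

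**Conclusion.** The point holds in a limited form. Two of eight post-intervention items presuppose a positive answer, none of the 12 items seeks negative experience directly, and the forms depart from the text in two places (mood in Section 4, negative effects in Section 6). The content analysis of acceptability may lean favourable as a result, and with no threshold set there is no numerical check on that reading.

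A reader might go further and conclude that the analysis is biased by a known amount. The documents give no basis for a size. Multiplying items by the 24 planned participants to set positive prompts against negative ones would not supply it, because a count of prompts does not measure bias and a selective count would omit most of the form. The doubt about favourable codes applies mainly to items 3 and 4.

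The conclusion assumes that the forms are administered as printed. If the online version already has a negative-effects question, that part is only a documentation gap, and the appendix should be brought into line. The change is worth making because it adds direct evidence on a primary objective at little cost.

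**What to change.** **Appendix 5**

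- Item 3: *What, if anything, did you like?*
- Item 4: *Was any of the information useful to you, or not?* with space for reasons.
- New item paired with these: *What, if anything, did you dislike or find unhelpful, or did you notice any negative effects from attending?* This also brings the form into line with Section 6. If the adverse event log needs a separate answer, print the two halves as two items.

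**Appendix 6**

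- Item 3: *Has your mood changed since the group (better / no change / worse)? Do you think Baby CHAT played a part?* This matches the description in Section 4.

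**Text**

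- Section 3, Statistics: state that positive and negative codes from the paired items will be reported side by side.
- Section 4: update the item count and the number of closed components.
- Section 6: point to the item that carries the negative-effects question.

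**Cost.** Three items are reworded and one is added. Comparability with the form from the earlier Baby CHAT trial falls slightly, but Section 4 says that form has already been adapted. The follow-up form was written for this study, so rewording it loses no comparison with the earlier trial.

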Appendix 7 – Baby CHAT Session Plan

1. (10 mins) Welcome

- Group facilitators introduce themselves and welcome to Baby CHAT, overview of Baby CHAT
- Confidentiality explained as well as limits to confidentiality (i.e. if we hear something that is of concern over group members safety or the safety of someone they know this would be shared with a third party – most likely their midwife and/or safeguarding lead).
- Ask every member of the group to write down on a post-it something they are looking forward to about meeting their baby.
- Ask every member of the group to say their name and if they feel comfortable share aloud what they wrote on their post-it.

2. (10 mins) Social and Unique baby (page 2 handout)

- Show pictures/videos of babies after birth - Trying to get people thinking about the uniqueness of babies and their developing social skills after they are born
e.g. video clip of Megan an 8-week old baby shown interacting first with her father, then with her mother. The video clip shows that an 8-week old baby is capable of reciprocal interaction with parents – when parents speak in high pitched tone, Megan kicks legs and makes noises (e.g. squealing with delight, laughing and babbling). Also shows Megan able to follow her mother with her head as her mother moves from side to side in front of her.
- ***All babies develop at slightly different times so this will not be the same for all babies***
- Discussion in pairs – what do people already know about a baby's social development and personality after birth? (Think about pictures/video clip/babies they know – try and think just after birth to about 6 months)
- Use flip chart paper/interactive white board to ask the group to feedback some of things they have been discussing. Feedback to group – flip chart paper/interactive whiteboard

The aim of this discussion is to get people thinking about baby's:

Personality

Temperament

Getting needs met

Smiling

Babbling

Crying – the purpose of this

Recognition- Moving head towards sounds/voice of mother/father

Preferences

Attention

Concentration

Awareness/baby cycles

Learning

Prompts for discussion if needed – draw attention to developmental timeline on page 2 of handout

Question for the group: When do you think this development of personality/social skills develops? Does it just happen as soon as the baby is born? Brief ideas about when this begin to occur i.e. before or after birth

3. (10 mins) Your own baby (page 3/4 handout)

- What have you learnt about your baby so far? (work through work sheet in pack)
- Temperament and personality

4. (10 mins) New research in this area – would you like to see some new images of babies being social in the womb?

- Social responsiveness of baby in womb - Show Video clip from [name]'s research
- Suggests that babies are developing their social skills while they are waiting to be born - not only are they getting physically ready for life after birth but they are developing the necessary social skills that they need to survive and interact with their caregivers.
- Getting ready for when they meet you!
- **What do you think your baby is doing in the womb? (page 5 handout)**

5. (15 mins) Implications of this for your pregnancy

- How can you make the most of this new information? What would help your baby to begin to develop social skills before they are born? (**pages 5-12 handout**)
- ***Important to emphasise to parents that there are no right or wrong answers when interacting with baby***
- So... what activities can you do?
- ***Important that these activities are sensitively stimulating i.e. finding a volume of music that is right for parent and baby* (page 6-12 handout)**

Think about baby's temperament/personality/routine

Pet name

Singing

Talking

Reading

Playing music

Massage

Relax/Mindfulness

- Work through at least one example
e.g. Give mindfulness meditation practice (on page 10 of handout)
- Plan when/where/how parents will have a go at one or more of these activities (**page 12 handout**)

6. (5mins) Ending – Ask everyone to write on a post-it something positive they will take away from the session about their baby's development.

Aim- to reinforce key messages and hopefully leave parents with positive feelings at the end of the group.
